Effects of sensorimotor training in patients with wrist osteoarthritis – a  
randomized controlled trial

2022-04-21

**Research group:** [name], RPT, MSc; [name], PhD; [name], PhD; [name], RPT, PhD. Skåne University Hospital, Malmö, Sweden.

Department of Translational Medicine, Lund University, Sweden.

**Authors:** as above.

**Background:** Patients with wrist osteoarthritis (OA) may suffer from pain, decreased range of motion (ROM) and reduced grip strength (1, 2). Although these impairments can have a significant impact on the patient's ability to perform daily activities and to participate in society (3), very little attention has been paid to specific rehabilitation regimes for this group of patients. The sensorimotor function in an OA affected joint can be disturbed with a negative effect on balance, muscle function, functional ability, and a changed movement pattern (4, 5). Exercises that focus on the sensorimotor control have shown good results in the treatment of other OA affected joints, such as knee and hip (4, 6). However, there are no previous studies that have evaluated the effects of sensorimotor training on wrist OA. Within this framework, we test the hypothesis that sensorimotor training improves the sensorimotor control, and thereby decrease pain and enhance functional ability, in patients with wrist OA.

**Aim:** The aim is to evaluate whether sensorimotor training is an effective treatment for patients with wrist osteoarthritis.

**Material and methods:** This study is a single-blinded randomized controlled trial (RCT) in patients with symptomatic and radiographically verified wrist OA with two treatment arms. The participants will be randomly assigned either to sensorimotor-control based exercises in combination with traditional OA treatment (i.e. joint protection with a wrist orthosis, range of motion (ROM) exercises, ergonomic advice, and modification of activities at work and leisure/task-specific training; *sensorimotor group*) or to ROM exercises only in combination with the previous mentioned traditional OA treatment (*control group*). The training will

consist of home exercises twice a day for three months. The treatments will be followed up by the treating physiotherapist at the department of hand surgery in Malmö, Sweden at 2-, 6- and 12-weeks post baseline, and the participants will be contacted by telephone at 4- and 8-weeks post baseline. Assessments will be performed at baseline and at 3, 6, and 12 months after baseline by an independent assessor, who is blinded to the participants' group allocation. At the 3- and 6-months follow-up, the participants will rate their global rating of change (GROC) regarding how they perceive their wrist pre- and post-training.

*Primary outcome:* Patient-Rated Wrist Evaluation (PRWE).

*Secondary outcomes:* Wrist range of motion (ROM), Numeric Pain Rating Scale (NPRS), Disabilities of the Arm, Shoulder and Hand (DASH) and General Self-Efficacy Scale (GSE).

*Statistical analysis plan:* Descriptive statistics [mean (SD) or median (minimum– maximum)] will be used to characterize the study groups. A power calculation has been performed with PRWE as the primary outcome, indicating that 48 participants will be sufficient to be included. To analyze potential differences between the groups, the Mann-Whitney test (for ordinal data) or independent sample t-test (for continuous data) may be used. The Wilcoxon signed-rank test or paired t-test may be used to analyze within-group differences. The level of statistical significance will be set at  $p \leq 0.05$ . All calculations will be performed using IBM SPSS Statistics version 28 (IBM Corporation, Armonk, NY, USA).

**Ethics:** The study was approved by the Swedish Ethical Review Authority, Dnr 2019-02437 and 2020-03807.

**Time plan:** Data collection 2019-2023. Analyzes and manuscript writing 2023-2024.

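### Does the trial fail to test its own hypothesis because no outcome measures sensorimotor control?

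*Combined protocol and SAP*

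**What the plan says.** The Background closes with the hypothesis: "we test the hypothesis that sensorimotor training improves the sensorimotor control, and thereby decrease pain and enhance functional ability". The next paragraph gives the Aim: "The aim is to evaluate whether sensorimotor training is an effective treatment for patients with wrist osteoarthritis".

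The primary outcome is PRWE. The secondary outcomes are "Wrist range of motion (ROM), Numeric Pain Rating Scale (NPRS), Disabilities of the Arm, Shoulder and Hand (DASH) and General Self-Efficacy Scale (GSE"). In addition, at the 3- and 6-month visits, "the participants will rate their global rating of change (GROC) regarding how they perceive their wrist pre- and post-training".

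Under Material and methods, one arm receives "sensorimotor-control based exercises in combination with traditional OA treatment", where the traditional treatment is described as including ROM exercises. The other arm is assigned "to ROM exercises only in combination with the previous mentioned traditional OA treatment".

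For group differences, the statistical analysis plan says that "the Mann-Whitney test (for ordinal data) or independent sample t-test (for continuous data) may be used". Wilcoxon signed-rank or paired t-tests are named for change within a group. The power calculation rests on PRWE and gives 48 participants.

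**The concern.** The Background sentence is worded as something the trial tests, not as background theory. It asserts that training improves control, that pain and function improve, and that the second happens because of the first. A reader who looks for the outcome that carries the first assertion finds none: no joint position sense, force sense or other neuromuscular measure is listed. ROM cannot stand in for one. It records how far the joint moves, and ROM exercises are given in both arms.

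If the sentence were the trial's operative objective, interpretation would suffer in two ways. A better PRWE in the sensorimotor arm might be reported as confirming the mechanism, when it would show only that allocation to those exercises helped. A null PRWE result could not distinguish training that failed to improve control from training that improved control without relieving symptoms.

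**Working it through.** There is no figure to recompute, since the point concerns whether the hypothesis, outcomes and analysis match. The check sets each part of the hypothesis against what is measured and analysed.

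| Part of the hypothesis | Listed outcome | Planned analysis |
|---|---|---|
| Training improves sensorimotor control | none | none |
| Training reduces pain | NPRS, PRWE | between-group test |
| Training improves function | DASH, PRWE | between-group test |
| The gain in pain and function runs through control | no mediator measured | no mediation analysis |

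**What is lost.** In the usual linear notation, write *a* for the effect of allocation on control, *b* for the effect of control on symptoms, and *c′* for the effect of allocation on symptoms by any other route. The total effect is

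*c* = *c′* + *a* × *b*.

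Without a measure of control, neither *a* nor *b* can be estimated, so both mediator links are untested. The total *c* needs no mediator: it is the difference between randomised groups in PRWE, NPRS or DASH. The pain and function parts of the hypothesis are therefore tested, and only the explanation of how they arise is not.

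**What the plan is built to answer.** The Aim asks about *c*. The primary outcome measures it, the power calculation is based on it, and the between-group tests estimate it. Neither the Aim, the outcome list nor the analysis plan promises a conclusion about *a*, *b* or their product.

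**What the contrast supports.** Both arms are described as receiving the same traditional treatment with ROM exercises, and the sensorimotor exercises are the described difference. A between-group difference would thus speak to the effect of adding those exercises. It would not identify why they work, and it would not rule out a contribution from extra exercise volume, because the document does not say that volume is matched.

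**What a change could achieve.** There are three options.

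1. *Add a measure of control.* The Time plan has data collection from 2019 to 2023 and the document is dated 2022-04-21. Participants enrolled before that date would have no baseline value.
2. *List a measure that is already being recorded.* Nothing in the document indicates that one exists.
3. *Reword the hypothesis to the effect on PRWE, pain and function, and keep the mechanism as rationale.* The result is close to the existing Aim with the comparator spelled out. No outcome, visit, test, estimate or error rate changes.

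**The case for a change.** The best case for a change is that an Aim silent on mechanism does not cancel a hypothesis that asserts one. The two statements differ, and only the Aim matches the outcomes. The primary outcome is patient-rated and the only party described as blinded is the assessor, so a PRWE difference could reflect expectation or additional exercise as well as better control. The Background says this training has not been evaluated in wrist OA before, so the document offers no wrist evidence for the mechanism either. Rewording costs nothing and would discourage over-reading of a positive result.

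Much of this stands. The mechanism is unmeasured, both links through it are untested, and a report of this trial should not claim to have shown it. Expectation and exercise volume are real limits on interpretation, but rewording the hypothesis would remove neither. The worry that the mechanism will be declared confirmed is a prediction about later reporting, and nothing in the plan commits the authors to that claim. The difficulty in explaining a null result is shared by any effectiveness trial that does not measure a mediator, and it leaves the primary inference unharmed. That rewording is cheap is not in itself a reason to amend when the correct objective is already on the same page.

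**Conclusion.** The mismatch is real but has no consequence for the plan. One Background sentence includes a mechanism with no outcome and no analysis behind it. The overall effects on pain and function, and the effectiveness question in the Aim, can be tested with PRWE, NPRS and DASH, and the primary comparison is unaffected. The size of the effect on estimates, error rates and sample size is nil.

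This rests on two readings: that the Aim, which the outcomes and analysis follow, is the operative objective and the Background sentence gives the theory behind it; and that no sensorimotor measure is being collected, since none is mentioned. An analyst working from this document would report the randomised differences and treat the mechanism as rationale, so no amendment is called for.

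### The planned between-group tests use no baseline covariate; they are valid, but ANCOVA on baseline PRWE would probably give more precision at almost no cost

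*Combined protocol and SAP*

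**What the plan says.** The Primary outcome entry names the PRWE. The Statistical analysis plan paragraph introduces the group comparison with "To analyze potential differences between the groups" and continues "the Mann-Whitney test (for ordinal data) or independent sample t-test (for continuous data) may be used". The only other tests are within-group: "The Wilcoxon signed-rank test or paired t-test may be used to analyze within-group differences". No ANCOVA, regression, mixed model or covariate appears in the document. It does not say whether PRWE counts as ordinal or continuous, or whether follow-up or change scores are compared.

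Material and methods gives the visits: "Assessments will be performed at baseline and at 3, 6, and 12 months after baseline by an independent assessor". Together with the planned paired tests, this implies that baseline PRWE is collected.

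On size, the plan says only "A power calculation has been performed with PRWE as the primary outcome, indicating that 48 participants will be sufficient to be included".

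**The concern.** A patient's baseline score on a questionnaire usually predicts the later score on the same questionnaire. A two-sample test on follow-up scores ignores that information. A test on change scores uses it, but fixes the coefficient of baseline at 1, whatever the data show. ANCOVA estimates the coefficient and removes the explained variation from the error term.

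The issue is efficiency, not validity. With 48 participants, the choice of analysis can decide whether a real PRWE difference is estimated usefully or is lost in a wide interval. The covariate is already being collected, so the precision can be had without more patients or visits.

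**Working it through.** **Inputs from the document.** N = 48, significance level 0.05, two randomised arms, visits at baseline and 3, 6 and 12 months.

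**Assumptions, because the document is silent.** 24 per arm, two-sided test, normal data, linear relation, equal SDs in arms and visits, no dropout, and a correlation ρ between baseline and follow-up PRWE ranging from 0 to 0.7.

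**The plan's own figure.** The 48 cannot be reproduced, because no difference, SD or power is given. It was back-solved instead: with 24 per arm, a follow-up t-test has 80% power at a standardised difference d = 0.826 and 90% at d = 0.956 (noncentral t, 46 df).

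**Variance of the group difference, in units of the follow-up variance**
- Follow-up t-test: 2/24, 46 df.
- Change-score t-test: (2/24) × 2(1 − ρ), 46 df.
- ANCOVA: (2/24) × (1 − ρ²) × (1 + 1/44), 45 df. The last factor is the cost of estimating one covariate.

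**Example, ρ = 0.5.** ANCOVA: 0.08333 × 0.75 × 1.0227 = 0.0639, SE 0.2528, half-width 2.014 × 0.2528 = 0.509 SD, noncentrality 0.826/0.2528 = 3.27, power 89.2%. Follow-up t-test: SE 0.2887, half-width 2.013 × 0.2887 = 0.581 SD, noncentrality 2.86, power 80.0%. The ratio 0.509/0.581 = 0.876 is a 12% narrower interval.

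**Power (%) at d = 0.826** (Mann-Whitney, MW, from 100,000 simulated trials)

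| ρ | ANCOVA | t, follow-up | t, change | MW, follow-up | MW, change |
|---|---|---|---|---|---|
| 0 | 79.1 | 80.0 | 50.9 | 77.3 | 48.5 |
| 0.1 | 79.5 | 80.0 | 55.1 | 77.3 | 52.4 |
| 0.3 | 82.7 | 80.0 | 65.8 | 77.3 | 62.9 |
| 0.5 | 89.2 | 80.0 | 80.0 | 77.3 | 77.3 |
| 0.6 | 93.3 | 80.0 | 87.9 | 77.3 | 86.0 |
| 0.7 | 97.2 | 80.0 | 95.1 | 77.3 | 93.9 |

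**95% CI half-width (SD), and the N that a follow-up t-test would need to match ANCOVA with 48**, that is 48/[(1 − ρ²)(1 + 1/44)]

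| ρ | ANCOVA | Follow-up | Change | Equivalent N |
|---|---|---|---|---|
| 0 | 0.588 | 0.581 | 0.822 | 46.9 |
| 0.1 | 0.585 | 0.581 | 0.780 | 47.4 |
| 0.3 | 0.561 | 0.581 | 0.688 | 51.6 |
| 0.5 | 0.509 | 0.581 | 0.581 | 62.6 |
| 0.6 | 0.470 | 0.581 | 0.520 | 73.3 |
| 0.7 | 0.420 | 0.581 | 0.450 | 92.0 |

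**Break-even.** Against follow-up scores, the ANCOVA interval is narrower once ρ exceeds 0.153.

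**Validity.** Simulated type I error was 4.7% to 5.3% for all tests examined.

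**Sensitivity**
- *Effect set for 90% power (d = 0.956).* At ρ = 0.3 / 0.5 / 0.7, ANCOVA has 91.9 / 95.9 / 99.4%, against 90% for follow-up scores and 78.2 / 90.0 / 98.7% for change scores.
- *20 per arm analysed, d = 0.826.* At ρ = 0.5, ANCOVA has 82.6% and either t-test 72.1%.
- *Unequal SDs.* With follow-up SD 1.25 times baseline SD and ρ = 0.7, the slope is 1.25 × 0.7 = 0.875. ANCOVA then gains nothing over change scores (half-width 0.420 v 0.419 follow-up SD; power 97.2 v 97.3%).
- *Skewed data (skewness 1).* At ρ = 0 / 0.1 / 0.3 / 0.5 / 0.6 / 0.7, MW on follow-up scores has 83 / 84 / 83 / 81 / 81 / 81% and ANCOVA 79 / 80 / 83 / 89 / 93 / 97%.

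**The case against.** The strongest objection is that the benefit depends on quantities the plan does not give. Several parts of it stand.

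- **The anchor matters.** If the trial was powered at 90%, the gain over follow-up scores at ρ = 0.3 / 0.5 / 0.7 is 1.9 / 5.9 / 9.4 points, not 2.7 / 9.2 / 17.2. If instead the 48 came from a change-score SD with 80% power, ANCOVA has 93.0 / 89.2 / 87.2 / 85.2 / 83.1% at ρ = 0.3 / 0.5 / 0.6 / 0.7 / 0.8, so the gain at high correlation is only 3 to 5 points.
- **The role of correlation depends on the comparator.** Against change scores with equal SDs, the variance ratio is (1 + ρ)/2 before the covariate penalty, so ANCOVA gains most when correlation is low. A need for moderate correlation applies to follow-up scores only.
- **A small reversal is possible.** At a slope of exactly 1 (SD ratio 1.25, ρ = 0.8), ANCOVA variance is about 2.3% larger than change-score variance, which widens the interval by about 1%.
- **Rank tests can win.** With skewed data and little correlation, Mann-Whitney on follow-up scores is about 4 points ahead. If the sponsor regards PRWE as ordinal, a mean difference is also a different quantity from a rank comparison.
- **The wording is permissive.** The plan does not exclude adjustment. But an adjusted model chosen after seeing group data would be open to challenge, so permissive wording does not replace prespecification.

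These points change the size of the gain. They do not reverse its direction at moderate correlation, and the losses they reveal are small next to the likely gains.

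**Conclusion.** The concern holds, as a matter of precision. The plan names no baseline covariate for the group comparison, while baseline PRWE should be available. Under the stated assumptions and at a correlation of 0.5, ANCOVA raises power from 80% to about 89%, and 48 participants do the work of about 63. At 0.3 the gain over follow-up scores is under 3 points; below about 0.15 there is a loss of at most about 1 point. The gain over change scores disappears when the slope is near 1.

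Confidence is high about what the text contains and about the direction at moderate correlation. It is not high about the size, which rests on an assumed correlation and a back-solved effect. The planned tests are not invalid or biased under randomisation with complete data. The change should be made, but the trial does not fail without it.

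**What to change.** Before group data are analysed, state that the primary between-group analysis is a linear model (ANCOVA) of PRWE on group and baseline PRWE, at one primary time point chosen by the sponsor. Report the adjusted mean difference in PRWE points with its 95% CI and p-value. Keep a rank-based analysis of PRWE as a sensitivity analysis, and keep the planned rank tests for ordinal secondary outcomes. Optionally, adjust continuous secondary outcomes for baseline and fit a mixed model over 3, 6 and 12 months.

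The cost is one or two sentences, one degree of freedom, residual checks and a little more work in SPSS. No new data are needed. The document is dated 2022-04-21 and data collection runs 2019-2023, so the change should be a dated amendment that records that no group comparison had been seen.

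### The only tests named for PRWE use just the participants seen at a visit, so earlier values are ignored, and the 6- and 12-month comparisons can be biased if loss differs between arms

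*Combined protocol and SAP*

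**What the plan says.** The Statistical analysis plan is a single paragraph. Between groups, "the Mann-Whitney test (for ordinal data) or independent sample t-test (for continuous data) may be used". Within groups, "The Wilcoxon signed-rank test or paired t-test may be used to analyze within-group differences". Material and methods describes a trial in "wrist OA with two treatment arms". The training will "consist of home exercises twice a day for three months", and "Assessments will be performed at baseline and at 3, 6, and 12 months after baseline by an independent assessor". PRWE is the primary outcome, with no primary time point. A power calculation is mentioned, "indicating that 48 participants will be sufficient to be included", without its inputs.

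The plan does not define an analysis set, say that participants are analysed as randomised, or name a missing-data method or a repeated-measures model. It does not say whether people who stop training are still assessed. No redaction accounts for these gaps.

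**The concern.** A two-sample test at 12 months uses only those with a 12-month value, and a paired test needs both values of the pair. A participant seen at baseline and 3 months but not at 12 months adds nothing to the 12-month comparison, although two PRWE values are in hand. The set analysed can also change from visit to visit.

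Randomisation protects the comparison of everyone randomised, not of those who remain. The last assessment falls nine months after training ends. Exercise content differs between arms, and only the assessor is described as blinded, so reasons for leaving could differ by arm. If participants doing badly at 3 months leave one arm more readily, that arm's remaining participants look better at 6 and 12 months for a reason unrelated to training. Depending on the arm, this creates a difference or hides one.

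**Working it through.** **Inputs from the documents.** 48 participants, two arms, visits at baseline, 3, 6 and 12 months, significance level 0.05.

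**Assumptions, because the documents give no figure.** 1:1 allocation (24 per arm), two-sided testing, PRWE SD 20, correlation 0.5 or 0.7 between any two visits, loss of 10% to 30%.

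**1. The plan's own figure.** The sample size of 48 cannot be reproduced, because power, target difference and SD are not stated. Working backwards at 80% power, it implies a difference of (1.960 + 0.842) × √(2/24) = 0.81 SD, or about 16 points if the SD is 20. If 48 holds no allowance for loss, 20% missing leaves 19.2 per arm. Power is then Φ(0.809/√(2/19.2) − 1.960) = Φ(0.547), about 71%. The same formula gives about 76% at 10% missing and 65% at 30%.

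**2. When completer tests are biased.** Let p be the share missing in an arm, and k the number of SDs by which its missing participants are worse than its completers. The completer mean then differs from the full-arm mean by p × k. With no true effect, the bias between arms A and B is pA·kA − pB·kB.

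- Same rate and same k in both arms: bias 0, false-positive rate 5%.
- Loss 30% against 10%, k = 0.5 in both: 0.20 × 0.5 = 0.10 SD, false-positive rate 6.1%.
- Loss 30% against 10%, k = 1.0 in both: 0.20 SD, false-positive rate 9.4%.
- Loss 20% in both, k = 1.0 in one arm and 0 in the other: 0.20 SD. The standard error is √(2/19.2) = 0.323 SD, so the shift is 0.20/0.323 = 0.62 standard errors. The false-positive rate is Φ(−1.96 + 0.62) + Φ(−1.96 − 0.62), about 9.5%.

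**3. A specific mechanism.** All loss occurs after month 3. In one arm it is random. In the other, those with the highest value of 3-month PRWE plus noise (SD 20) leave. The correlation of that score with 3-month PRWE is 20/√(20² + 20²) = 0.707.

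With 20% leaving, the mean score of those who stay is φ(0.842)/0.8 = 0.280/0.8 = 0.350 SD below the full-arm mean. Their mean 3-month PRWE is 0.350 × 0.707 × 20 = 4.95 points too low. Their 12-month mean is too low by 4.95 × 0.5 = 2.5 points or 4.95 × 0.7 = 3.5 points.

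With 2 of 24 leaving (about 10%), the factor is φ(1.383)/0.917 = 0.167, and the bias is 0.167 × 14.14 × 0.5 = 1.2 points or, with 0.7, 1.7 points.

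Simulation with no true effect (8,000 replicates) agrees:

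| Loss in each arm | t-test bias, correlation 0.5 / 0.7 | False-positive rate |
|---|---|---|
| 10% | 1.1 / 1.6 points | 5.7% / 5.8% |
| 20% | 2.4 / 3.5 points | 6.3% / 8.7% |
| 30% | 3.2 / 4.6 points | 8.3% / 11.0% |

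In the same settings, a pooled likelihood analysis that keeps the baseline and 3-month values has bias of about 0.2 points or less, a false-positive rate of about 4% to 5%, and an empirical standard error 10% to 28% smaller than the t-test's. Most of that gain comes from using baseline: √(1 − 0.5²) = 0.87 and √(1 − 0.7²) = 0.71. The removal of bias comes from keeping the 3-month values.

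**4. The symmetric case.** With the same outcome-related loss in both arms, t-test bias is within about 0.13 points of zero and the rejection rate is 5.1% to 6.0% at every loss level and both correlations.

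**The case against.** The strongest reply is that the bias figures come from a chosen asymmetry. Both arms do home exercises, share the traditional treatment and follow one visit schedule. If people leave at the same rate for the same reasons, the completer comparison is close to unbiased. That stands. The documents give no attrition figure by arm, so they do not support a statement that this trial's result will be biased, only that the named tests give no protection if loss is uneven.

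Four further inferences are tempting and not supported.

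- A reader might infer that people who stop training are to be excluded. The assessments are not made conditional on continued training; the plan is silent on this.
- A reader might treat the home exercise as unsupervised. The physiotherapist follows participants up at weeks 2, 6 and 12, with telephone contact at weeks 4 and 8. These contacts end with the training period and do not reach the 6- and 12-month visits.
- A reader might carry the figures over to 3 months. They assume all loss comes later. The 3-month tests also use only those seen, but a participant lost before then has only a baseline value, from which any model recovers little.
- A reader might infer that 48 includes no allowance for loss. The inputs are not given, so this cannot be known.

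It is also true that the permissive wording (the tests may be used) rules out neither imputation nor a model. But it plans neither, and handling of losses could be chosen after the data are seen. Multiple imputation would be an acceptable alternative to a mixed model.

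**Conclusion.** The concern holds in a limited form. The plan's only named analyses discard PRWE values already collected from anyone who later misses a visit. The loss of precision follows from the choice of tests. Bias at 6 and 12 months is conditional on loss that differs between arms in rate or in its relation to outcome.

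Under the asymmetric illustration, 20% loss biases the 12-month t-test by about 2.5 to 3.5 points. That is roughly 15% to 22% of the 16-point difference implied by 48 participants at 80% power and SD 20 (2.5/16.2 and 3.5/16.2). The false-positive rate is about 6.5% to 9%. At 10% loss the bias is small, about 1 to 1.7 points. All sizes rest on the assumed SD, correlation, allocation, loss and mechanism. A better analysis is available in the software already named, so the change is worth making even if losses prove few.

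**What to change.** Make the main PRWE analysis one linear mixed model for repeated measures in SPSS:

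- all randomised participants, in the group to which they were randomised, using every PRWE value collected;
- baseline, 3-, 6- and 12-month PRWE as responses;
- visit and group-by-visit effects, with a common baseline mean for the two groups;
- unstructured covariance and small-sample degrees of freedom;
- group differences with confidence intervals at each follow-up visit.

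Keep the named tests as a completer sensitivity analysis, and report losses and reasons by arm and visit. State whether participants who stop training are still assessed. Fix this wording before group comparisons are seen; the Time plan places analysis in 2023-2024, after data collection.

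The cost is SAP wording and slightly more analysis work, with no extra participants or visits. The model treats PRWE as continuous, as the t-test does. It relies on data being missing at random given the observed values, a weaker assumption than the completer tests need but still an assumption. It recovers little for participants with only a baseline value, and it cannot restore visits already missed.
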